morphology of the maxillary molars and to ascertain its ability to visualize the second mesiobuccal canal (MB2). **Betancourt et al 2016** have examined the geometric location in depth. They described in vivo the prevalence and location of the MB2 in the mesiobuccal root of the first maxillary molar (1MM) and the second maxillary molar (2MM) through CBCT imaging. In the 1MM protocol, the prevalence of the MB2 canal was 69.82% and was more frequent in women (p = 0.005). They concluded that CBCT is a high-precision diagnostic tool for not only detecting but also locating in vivo the MB2 canal in the mesiobuccal root of upper molars.

Aim of the Study

The aim of the study is to estimate the prevalence of a second mesiobuccal canal of maxillary first and second molars in Egyptian population.

Population: Egyptian population

Outcome Variable: Presence or absence of a second mesiobuccal canal of

maxillary first and second molars

	Outcome	Measuring Device	Measuring Unit	
	Measured			
Primary Outcome	Presence of a second mesiobuccal canal of maxillary first and second molars	CBCT Software (On Demand 3D®)	Binary System (Yes/No)	
Secondary Outcome	Prevalence in the whole sample (females and males)		Percentage	

Research question:

What is the percentage of presence of a second mesiobuccal canal in Maxillary First and Second Molars among Egyptian Population?

Materials and Methods

Study Design: Cross-sectional Study

Setting and Location:

- 1- The data collection will be obtained from the data base available at a private radiographic centre ORASCAN Oral & Maxillofacial Imaging Centre located in Cairo, Egypt.
- 2- CBCT images will be obtained from Egyptian patients who had CBCT examination as part of their dental examination, diagnosis or treatment planning during the years 2015-16-17.

Participants:

A total of 196 CBCT scans of Maxillary first and second permanent molars belonging to Egyptian individuals will be included.

Images of the first and second maxillary permanent molars are selected according to the following **Inclusion criteria:**

- First and second maxillary permanent molars of Egyptian patients starting from 15 years, males or females
- Intact roots without fractures or cracks
- Molars without posts or previous root canal treatment
- CBCT scans of maxillary first and second molars using 8 × 6 FOV, 0.2 voxel resolution

Exclusion criteria:

- Evidence of apicectomy or periapical surgery
- Odontogenic or non-odontogenic pathology

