- Maxillary molars with developmental anomalies

- External or Internal Root resorption
- Canal Calcification
- Previous root canal treatment
- Extensive coronal restorations
- Posts or crown restorations
- Root caries specially reaching the trifurcation area
- Tomographic images of poor quality or artifacts interfering with the detection of root canals

Variables:

- 1. Number of root canals in mesiobuccal root of first and second maxillary molars
- 2. Sex of the patient will be identified and addressed as the prevalence of the second mesiobuccal canal may show sex predilection

Data Sources / Measurements:

Retrospective Data Analysis will be performed after the CBCT images are pooled from the computer database.

All the CBCT examinations were scanned using Cranex® 3D SOREDEX, 0.2 voxel resolution, 8 × 6 cm FOV, 90 kVp, 10 mA and 6 seconds exposure time.

CBCT images will be analysed in the 3 planes; first the sagittal and coronal sections will be oriented parallel to the long axis of the root, and then sections will be obtained on the axial plane for detection of the 2nd mesiobuccal canal (Betancourt et al 2016).

CBCT images will be interpreted by three oral radiologists independently; blinded from demographic data of the patients and from the results of each other.

Each one will evaluate the images separately twice with a period of two weeks between the two reading sessions.

Then inter-observational and intra-observational variability between the observers will be evaluated.

The sex of the patient will be identified from the patient's demographic data available on the patient's file on the database of the private radiographic centre.

Bias:

No source of bias.

Study Size:

The aim of the study is to assess the prevalence of a second mesiobuccal canal of maxillary first and second molars in Egyptian population. Based on the previous paper by Nikoloudaki et al, 2015, the prevalence of Second Mesiobuccal Canal of Maxillary First and Second Molars was 89 and 85%. Using a precision of 5, a design effect set at 1 with 95% CI (confidence interval), a total sample size of 196 will be sufficient. The sample size was calculated by Epi info.

Sampling Strategy: The sample will be collected by simple random sampling.

Quantitative Variables:

The number of CBCT scans of Egyptian individuals with second mesiobuccal canal will be counted to estimate the prevalence of the second mesiobuccal canal.

Statistical Methods:

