- 1- Data will be analysed using IBM SPSS advanced statistics (Statistical Package for Social Sciences), version 21 (SPSS Inc., Chicago, IL). Numerical data will be described as mean and standard deviation or median and range. Categorical data will be described as numbers and percentages. Comparisons between male and females for normally distributed numeric variables will be done using the Student's t-test while for non-normally distributed numeric variables will be done by Mann-Whitney test. Comparisons between categorical variables will be performed using the chi square test. A p-value less than or equal to 0.05 will be considered statistically significant. All tests will be two tailed.
- 2- If the patient's age couldn't be found in the patient's file, the dental age will be used.
- 3- If the patient's sex couldn't be found in the patient's file, the patient's name will be used to indicate the sex. Patients with mixed name will be excluded.

References

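### The sex comparison of MB2 is an unadjusted chi-square, so a male/female age difference in the archive, if there is one and if age affects whether MB2 is seen, would go uncorrected

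*Combined protocol and SAP*

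**What the plan says.** All references are to the combined protocol and SAP.

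- **Variables.** Sex is one of two listed variables: "Sex of the patient will be identified and addressed as the prevalence of the second mesiobuccal canal may show sex predilection". Age is not listed.
- **Statistical Methods, item 1.** "Comparisons between categorical variables will be performed using the chi square test". The threshold is "A p-value less than or equal to 0.05 will be considered statistically significant", and "All tests will be two tailed". Numeric variables are compared between the sexes by t-test or Mann-Whitney test. No regression, stratification or matching appears anywhere.
- **Inclusion criteria.** "First and second maxillary permanent molars of Egyptian patients starting from 15 years, males or females", with no upper limit.
- **Statistical Methods, item 2.** "If the patient's age couldn't be found in the patient's file, the dental age will be used". With the entry rule, this implies some age value for every patient.
- **Exclusion criteria.** The list includes "Canal Calcification", and images whose quality or artefacts prevent canals from being read.
- **Setting and Sampling Strategy.** Scans were taken for clinical reasons at one private centre and are drawn by simple random sampling.
- **Bias.** The section states that there is none, so confounding is not discussed.

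**The concern.** Sex is the only characteristic whose association with MB2 the plan sets out to examine, and the literature review cites a significant sex difference (p = 0.005) for first molars. A reader of the report is therefore likely to take the chi-square result as the answer on sex predilection.

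Simple random sampling from an archive reproduces the archive's age mix within each sex and does not balance it. If women and men were scanned at different ages, and MB2 is seen less often at some ages than at others, a crude test attributes the age difference to sex. With no true sex effect, this raises the false-positive rate. With a true effect, it can hide it or exaggerate it. The t-test or Mann-Whitney provision could show an age imbalance but would not correct the comparison for it.

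**Working it through.** **1. The plan's own figure.** Study Size gives the planning prevalence: "the prevalence of Second Mesiobuccal Canal of Maxillary First and Second Molars was 89 and 85" per cent, with precision 5 points, 95% confidence and design effect 1. At p = 0.85, n = 1.96² × 0.85 × 0.15 / 0.05² = 195.9, rounded up to 196. The stated size reproduces. It is a precision calculation for prevalence and attaches no power to the sex comparison.

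**2. Inputs for the confounding check.** From the documents: n = 196, two-sided 0.05, chi-square. Assumed, because the documents give none of these: 98 women and 98 men with one yes/no result each, the age mix within each sex, and the MB2 percentage by age band. There is no true sex effect within any band.

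**3. Formula.** Expected prevalence in each sex is the sum over bands of (share in band × MB2 rate in band). With spurious gap d and mean prevalence p̄:

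- SE0 = √[2p̄(1 − p̄)/98]
- SE1 = √[pF(1 − pF)/98 + pM(1 − pM)/98]
- Rejection rate = Φ[(d − 1.96·SE0)/SE1] + Φ[(−d − 1.96·SE0)/SE1]

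Example, with MB2 seen in 90/80/65% (young/middle/older):

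- Women 45/35/20%: 0.45×90 + 0.35×80 + 0.20×65 = 81.5%.
- Men 30/35/35%: 0.30×90 + 0.35×80 + 0.35×65 = 77.75%.
- d = 3.75 points, p̄ = 79.6%, SE0 = SE1 = 5.75 points; rejection rate 10.0%.

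**4. Results across assumptions, by the formula.**

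| MB2 seen by age band | Age mix, women vs men | Spurious gap (points) | Crude false-positive rate |
|---|---|---|---|
| any | identical | 0 | 5.0% |
| 90/80/65% | 40/35/25 vs 35/35/30 | 1.25 | 5.5% |
| 90/87/82% | 45/35/20 vs 30/35/35 | 1.2 | 5.7% |
| 90/86/80% | 45/35/20 vs 30/35/35 | 1.5 | 6.0% |
| 90/80% (two bands) | 40% vs 60% older | 2.0 | 6.8% |
| 90/87/82% | 55/30/15 vs 25/35/40 | 2.15 | 7.3% |
| 90/86/80% | 55/30/15 vs 25/35/40 | 2.7 | 8.4% |
| 90/80/65% | 45/35/20 vs 30/35/35 | 3.75 | 10.0% |
| 90/70% (two bands) | 40% vs 60% older | 4.0 | 10.7% |
| 90/80% (two bands) | 30% vs 70% older | 4.0 | 12.2% |
| 90/70% (two bands) | 30% vs 70% older | 8.0 | 28.7% |
| 92/80/60% | 55/30/15 vs 25/35/40 | 8.6 | 31.7% |

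**5. With age in the analysis, by simulation.** Logistic regression on sex and age (4,000 runs per scenario) rejected in 4.6% of runs for 90/80/65% with the 45/35/20 vs 30/35/35 mix (crude 10.4%). It rejected in 5.1% for 92/80/60% with the 55/30/15 vs 25/35/40 mix (crude 30.6%), and in 4.9% with equal mixes (crude 4.9%). An age-stratified Mantel-Haenszel test (1,500 runs per scenario) stayed between 4.8% and 5.6% in the four two-band scenarios above and in one with no age effect.

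**6. Masking.** Take a true 15-point advantage for women and 90/70% by age, shifted by ±7.5 points for sex. Power from 1,500 simulated runs:

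| Older women vs men | Crude gap (points) | Chi-square | Mantel-Haenszel |
|---|---|---|---|
| 50% vs 50% | 15 | 77% | 79% |
| 60% vs 40% | 11 | 48% | 75% |
| 70% vs 30% | 7 | 25% | 69% |

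**The case against.** **Both links are assumed.** Confounding needs an age-MB2 relation and a sex-age imbalance. The documents report neither; the literature review mentions sex and study method as sources of variation, not age. This stands. A reader might infer that the planned sex comparison is biased, or that the archive's men and women do differ in age. The documents support only that such a difference would go uncorrected.

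**The design already closes part of the pathway.** Calcified canals are excluded, as are extensive restorations, resorption and unreadable images. This also stands in part. Any age effect short of exclusion remains, and a canal too obliterated to be seen may simply be scored as absent.

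**The large figures need large inputs.** The 10% and 32% results from the three-band scenarios rest on falls of 25 and 32 points in MB2 detection across age, with mean prevalence near 79-80%, below the planned 85-89%. Age effects nearer the planning figures give about 6-8%. This stands, and is why the range must be shown whole.

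**The comparison is subsidiary.** The aim and primary outcome are prevalence, and a crude contrast is a legitimate description of the sample. Correct, so the crude test should stay; it does not justify a statement about sex predilection when the age mix has not been examined.

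**Age may not be fully known.** That age is recorded for every patient would be too strong a reading. The fallback implies that some files lack it, and the plan does not say how dental age would place an adult in an age band. This limits the adjustment for those patients but is no reason to leave age out.

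**Conclusion.** The point holds in a conditional form. The plan tests sex predilection with a crude chi-square only and names no use of an age value that it implies for each patient. If the archive's men and women differ in age and age affects whether MB2 is seen, the false-positive rate of the sex test would be about 5.5-8% under small effects, 10-12% under moderate ones and about 30% only under strong ones. Age adjustment gave about 5% in every scenario in which it was simulated. If either link is absent, the crude test keeps its 5%.

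These figures rest on 98 patients per sex, one result per patient, and assumed age mixes and age effects. A reader might infer that the main result is also in doubt. Nothing here supports that: the overall prevalence estimate does not depend on the sex comparison, and 196 reproduces from the plan's inputs. This is a cheap improvement to a secondary analysis.

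**What to change.** 1. **Variables:** add age, with a flag for patients whose age is a dental-age substitute.
2. **Statistical Methods, item 1:** report the age distribution by sex. Add a logistic regression of MB2 on sex and age (or an age-stratified Mantel-Haenszel test). Report the age-adjusted sex effect with its 95% CI beside the crude chi-square, and qualify any statement on sex predilection if the two differ.
3. **Sensitivity:** repeat the model without the flagged patients.
4. If the analysis is run per molar, include age in that model in the same way.

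The cost is a few sentences and one extra model (run twice) in the software already named. No new scans or readers are needed, and age is largely available from applying the entry rule. The downside is imprecise age for patients with a dental-age substitute, which the flag and the repeat analysis make visible. Fixing the covariate now also avoids choosing it after the data are seen.
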